
Section: Section 1 - Objective, Aims, Background and Significance

(a similar weight-bearing anatomic region) can be performed safely and effectively with retention rates approximating 75% up to 2 years and beyond (27-29). In an OVID database search of fat grafting articles, over 9000 articles have referenced the use of fat grafts in a wide arena of clinical situations. Specifically to this application over 100 references were relevant to this proposal and provided below.(30-136)Clinically, atrophied fat pads in the weight bearing foot were replaced or supplemented with fat grafts. [Chairman EL. Restoration of the plantar fat pad with autolipotransplantation; J Foot Ankle Surg. 1994 Jul-Aug;33(4):373-9] This procedure was shown to be safe, efficacious and had long term benefits. We propose a clinical trial to assess the efficacy of minimally invasive autologous fat transfer to address pain and poor prosthetic fit at amputation sites. We plan to randomize 15 subjects to the standard fat grafting surgical procedure which involves the immediate transplantation of a subject's own tissue and does not require FDA oversight. Additionally, we will use our knowledge and expertise working with adipose stromal cells to compare a regenerative medicine cell therapy modification of the fat grafting procedure with more traditional fat graft preparations. We plan to randomize 15 subjects to the enriched adipose stromal cells using the Tissue Gensis Cell Isolation System (CIS) IDE # (pending) to process the cells for the modification of the fat grafting procedure. The PI not only has experience with fat grafting in his clinical practice, but also serves as principal investigator in a clinical trial assessing the impact of facial fat grafting for wounded military personnel. The Biomedical Translational Initiative (BTI) (Structural fat Grafting for Craniofacial Trauma, W911QY-09-R-0030) from the Office of the Assistant Secretary of Defense involves the treatment of 20 wounded warriors with facial injuries using minimally invasive fat grafting techniques. This study has established significant infrastructure to evaluate soft tissue reconstruction after facial trauma, and demonstrates the ability of the PI to assemble and manage the team for an interdisciplinary clinical trial. This study, still in progress, has treated 15 subjects out of a targeted enrollment of 20 subjects with no serious adverse events and improved outcomes in all subjects. Another phase of this trial, currently funded through the Armed Forces Institute of Regenerative Medicine (AFIRM) clinical trials program and starting to recruit subjects, assesses the efficacy of a regenerative medicine approach of enriching the fat graft with autologous adipose stromal cells. That same intervention will be trialed in this study, as well. The biggest problem associated with fat grafting is unpredictable rates of fat graft resorption. This is likely related to the ability of the regenerating adipose tissue to rapidly develop a new blood supply. This study will examine if fat grafting with cell enrichment will demonstrate increased fat retention and decreased pain compared to standard fat grafting alone. A modified preparation of the fat graft involves concentrating the endogenous stromal cells in the graft material in an effort to increase graft retention over time. The aspirated fat material used for fat grafting consists of mature adipocytes, a small amount of fibrous tissue, and immature adipose stromal vascular fraction cells (SVFs). These adipose stromal cells are a mixed population of non-lipid laden cells that serve to turn over mature adipocytes and vascular elements. One cell type, "Preadipocytes," or adipose derived stem cells (ASC's), as well as endothelial precursor cells and multilineage

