in the current FDA-approved product labeling for that device (i.e., for an “off-label” indication)?

* No

- 2.2.2.1.1 List each of the devices being evaluated for an “off-label” indication. Specify for each listed device the corresponding Investigational Device Exemption (IDE) number for this device/research study; or provide a justification for why you feel that this device and its “off-label” use, as proposed in this research study (i.e., to include potential failure of the device) constitute a non-significant risk to the involved research subjects.

*

| Device | IDE # | Non-significant risk justification |
|--------|-------|------------------------------------|
|--------|-------|------------------------------------|

There are no items to display

[reviewer notes-]

Section 2 - Research Design and Methods

- 2.3 Summarize the general classification (e.g., descriptive, experimental) and methodological design (e.g., observational, cross-sectional, longitudinal, randomized, open-label single-blind, double-blind, placebo-controlled, active treatment controlled, parallel arm, cross-over arm) of the proposed research study, as applicable.

Prospective, Randomized, Non-blinded, Surgical outcomes, Pilot study assessing clinical outcomes following fat grafting for pain at amputation sites (with and without adipose stem cell enrichment).

- 2.3.1 Does this research study involve a placebo-controlled arm?

* No

[reviewer notes-]

Section 2 - Research Design and Methods

- 2.4 Will any research subjects be withdrawn from known effective therapy for the purpose of participating in this research study?

Section: Section 2 - Research Design and Methods

* No

- 2.4.1 Provide a justification for discontinuing subjects from known effective therapy for the purpose of study participation.
- 2.4.2 Describe the risks to subjects associated with discontinuing them from known effective therapy for the purpose of study participation.

[reviewer notes-]

Section 2 - Research Design and Methods

- 2.5 Will screening procedures (i.e., procedures to determine research subject eligibility) be performed specifically for the purpose of this research study?

* Yes

- 2.5.1 List the screening procedures that will be performed for the purpose of this research study. Do NOT include the inclusion/exclusion criteria in this section as they will be addressed in section 3; questions 3.13 and 3.14.

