
recordings. 3.) All participants who are women of child bearing potential will receive a urine pregnancy dip test. If the test result is positive the subject will not continue participation in this research study. 4.) Collection and review of new medications to include prescription and vitamins / supplements, allergies and vital signs (Temp, HR, Resp, BP), weight, body mass index (BMI) calculation, and adverse event reporting. 5.) Serial Computed Tomography Imaging or MRI scan will be performed. A high resolution Computed Tomography (CT) Scan of the amputation stump will be performed at Presbyterian Hospital and will take approximately 60 minutes. This scan will be pre-procedural and will serve as a baseline. All CT scans will be performed on a 64-slice scanner (LightSpeed, GE Healthcare), using slice thickness of 1.25 mm and pitch of 1.375. kVp, mA, and FOV will be optimized to the subject and body part to be imaged. Soft tissue and bone kernels will be employed. These images will be volumetrically reformatted into coronal and sagittal planes for confirmation of findings. Additionally, surface-rendered volumetric reformats will be created emphasizing both bony structures and soft tissues. In the event that a CT scan is contraindicated or declined by a study participant, MRI will be performed using a 1.5 T MRI scanner (Signa HDx, GE Healthcare). The MR imaging protocols will include coronal and axial planes using T1-weighted spin echo sequences as well as coronal, axial, and sagittal planes using T2-weighted fast spin echo with fat suppression and/or short tau inversion recovery (STIR) sequences. Again, FOV, TR/TE time, acquisition time and other parameters will be optimized to the subject and body part to be imaged. Intravenous contrast will not be administered for either CT or MR imaging. Images will be reviewed by radiology. Volume measurements of the implanted material will be made on all post-procedural CTs or MRIs. These volumetric measurements are expected to be precise to within 5% of the actual volume of material. Trends in volume of tissue will be analyzed over time across the multiple CT or MRI scans. Both linear and volumetric measurements will be used to quantify implanted material. Subjects must remove compression sleeves prior to CT scans. 6.) To further evaluate pre-surgical amputation stump pain, the study coordinator will provide a Pain Assessment form to the participant to complete. This form will document the nature/charter of the discomfort limiting function and or interferes with their ability to use a prosthetic device. The subject will be instructed to document the discomfort to include frequency, location, intensity (1 to 10 scale with 10 as most intense), type of pain (physiological or phantom). It will include self interventions related to pain and use of prosthetic devices. 7.) Psychosocial Assessment: One of the aims of the proposed study is to evaluate pre- and post-operative quality of life and symptoms of psychological distress. This aim will also consider psychosocial factors (pre- and post- surgery) that predict psychological well-being and quality of life outcomes following surgery. The aim is important for identification of psychosocial factors that may play a role in and be critical to enhancing quality of life outcomes from amputation stump surgery. Participants will be asked to complete a psychosocial battery that includes: a) self-report measures of satisfaction with physical appearance, anxiety and depressive symptoms, social functioning and social avoidance and distress and; b) questionnaires that assess significant predictors of quality of life

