
Section: Section 2 - Research Design and Methods

Montefiore Hospitals within the operating room suites. In brief, fat tissue to be used for grafting is harvested (usually from abdomen or thighs) with a small liposuction cannula in the operating room. Specific details of the Fat Harvest and Graft Preparation follow: Subjects will receive general anesthesia or a block with sedation. A dilute epinephrine solution (concentration 1:1,000,000) will be injected into the harvest site, which is usually abdominal or thigh subcutaneous tissue. A blunt tip hollow cannula is then used to aspirate through 5mm incisions. Up to 1500cc of lipoaspirate solution mixture will be obtained. This mixture once centrifuged is anticipated to produce an adequate volume of concentrated adipose tissue for injection, cell processing, and research assays. For the 15 subjects randomized to the Autologous Standard fat graft processing we will prepare the fat graft as follows: Once harvested the aspirated fat tissue will be processed as standard graft material. It will be divided into small aliquots and centrifuged in a sterile rotor (3000 rpm for 3 minutes/1200g), and top fluid oil layer from the fat tissue fractions were removed, and transferred into 3mL syringes, each filled with 2.5mL of the lipoaspirate and injected into the amputation stump. This graft preparation will be performed in the operating room. Standard fat graft material will serve as a control treatment and will be injected into limb using specialized injection cannulas as described below ("Fat Graft Placement"). For the 15 subjects randomized to the Autologous Fat Graft enhanced with adipose stromal cell processing we will prepare the cells as follows: Approximately 60-150 cc of lipoaspirate will be collected from the subject to be processed at the HSC lab using the Tissue Genesis Cell Isolation System™ (CIS) to yield approximately 3-8cc of Stromal Vascular Fraction (SVF) suspension. Per the Principal Investigator's clinical evaluation of the area of deficit as it relates to the amount of fat volume necessary to appropriately fill the deficit, the team may employ a second Tissue Genesis Cell Isolation System™ (CIS) concurrently. The aspirated fat processed as standard graft material will be divided into small aliquots and centrifuged in a sterile rotor (3000 rpm for 3 minutes/1200g), and allowed to decant before separating the fluid and oil layers from the fat tissue fractions, and transferred into 60 ml syringes. This graft preparation will be performed in the operating room. a. The lipoaspirate for concentration along with a 5cc aqueous solution syringe for each 60 cc syringe will be transported from the operating room to the Hematopoietic Stem Cell Laboratory (HSC Lab) at the UPMC Hillman Cancer Center, [name]. This facility is directly across the street from the operating room and connected via a connecting bridge. No specimen during transport will be transported outside of a building(s). In brief, this is a state-of-the-art laboratory that was constructed of materials compliant with 21 CFR 211, has a cleanroom that is ISO Class 6, and is GMP compliant with regards to function. This facility is registered with the FDA (FEI# 3004565478), is FACT accredited (since 1999) and is CAP accredited (CAP LAP # 7190853).b. In the Hematopoietic Stem Cell Laboratory (HSC Lab), the stromal vascular fraction (SVF) cell suspension (device output) will be processed using the Tissue Genesis Cell Isolation System™ according to procedures and a cell count will be performed as described in SOP 2008-02-R0. Prior to administration to of the SVF to the subject, rapid endotoxin testing, cell viability, cell count determinations and Gram staining will be

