
performed as described in SOPs 2005-13-R5 [SOPs are Attached] and 2008-02-R0. The acceptable endpoints are: AO viability \geq 50%; Endotoxin levels $<$ 5EU/kg of recipient ideal body weight, cell yields \geq 1E+05 total SVF cells per mL of adipose stroma and gram stain negative. The determinations will be recorded in triplicate. All handling and procedures with the lipoaspirates and isolation of the SVF are handled in sterile areas and all personnel are appropriately gowned and gloved as well as all laboratory instruments (pipettes, etc.) have been appropriately sterilized/cleaned. c. The released adipose stromal vascular fraction preparation will be transported back to the operating room. The concentrated autologous stromal vascular fraction cells will arrive back in the operating room close to the time that the standard fat graft preparation process is completed. It is anticipated that the time required for preparing the Autologous Stromal cells concentrated fat graft will add no more than 30 minutes to the overall operating time compared to Autologous Standard fat graft processing. d. The Standard graft material and the stromal vascular fraction cells will be mixed and subsequently injected into the amputated stump a target concentration of $2.0 - 3.0 \times 10^6$ stromal vascular cells/ml of injected fat graft is desired in this study. However, we recognize that there will be significant variation in cell yield between patients, as well as variation in required graft volumes. The actual cell dose for each subject will be collected to the intraoperative source document. The procedure for combining the SVF with the lipoaspirate prepared in the operating room will be performed inside the sterile operating room by [name] or a co-investigator who is specifically trained in the techniques of fat graft processing using the [name] method as well as this cell-enrichment technique of combining SVF with lipoaspirate. i. To manually combine the standard fat graft material and the SVF suspension (device output), each of the syringes will be connected via luer to luer lock. The contents of the lipoaspirate syringe are transferred to the SVF syringe and the cell suspension will be injected slowly back and forth between the two (2) syringes. The final 1 mL SVF-fat graft syringe is now considered cell-enriched and ready for injection into the subject. ii. It should be noted that in the event of fat harvest from both abdomen and thigh, abdominal fat grafts will be combined with abdominal fat SVF and thigh fat grafts will be combined with thigh fat SVF. Fat Graft Placement: The plastic surgeon will use the specially designed hollow injection cannulas (smaller diameter cannulas with varied shapes and tip sizes specifically made to deliver smaller amounts of fat) to fill the desired areas with the designated portion of fat. Incisions for cannula sites average less than 5 mm. The [name] Cannula System is not experimental and is commercially available in the United States and in compliance with Federal regulations for surgical instruments. A maximum fat graft volume, to include control grafts and SVF-concentrated grafts, of 300mL will be injected. The graft volume necessary to treat the stump site will be determined by the clinical judgment of [name]. They are plastic surgeons who have significant experience in fat grafting techniques. In addition, previous high-resolution 3D CT scans will be used to help determine the fat volume needed to treat. As is standard of care for fat grafting, the fat will be injected in small 3mL syringes to prevent excessive ischemia that may otherwise be seen with larger graft volumes. If additional SVF

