2.15.3 Will biological specimens be stored without identifiers or linkage codes? *

[reviewer notes-]

Section 2 - Research Design and Methods

2.16 Will research participants be asked to provide information about their family members or acquaintances?

* No

2.16.1 Describe what information about the third party will be obtained from the participant:

2.16.2 If the information about the third party is of a private nature, can the identity of the third party be readily ascertained or associated with this information?

*

Describe the private information that will be collected and recorded about the third party:

[reviewer notes-]

Section 2 - Research Design and Methods

Section: Section 2 - Research Design and Methods

2.17

What are the main outcome variables that will be evaluated in this study?

Primary outcomes: Improvement of pain at the amputation site, improved ability to tolerate a prosthesis, and generation of a stable volume of adipose tissue at the amputation site (as measured by clinical assessment by rehabilitation sciences and prosthetics team, quality of life measures, and high resolution imaging). This will be compared between the standard fat grafting group (n=15) and the adipose cell enriched fat grafting group (n=15). Secondary outcomes: Local and systemic complications resulting from fat graft procedure (infection, fat necrosis, hematoma, seroma); basic assays of adipose cell behavior to elucidate the functional properties of adipose cells used for grafting, with correlation to outcomes.

2.18

Describe the statistical approaches that will be used to analyze the study data.

* Addressed below:

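### Patients are not masked, although pain and five of eight prosthetic assessments rest on their own report and nothing they undergo requires them to know their arm

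*Combined protocol and SAP*

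**What the plan says.** Section 2.3 gives the design as "Prospective, Randomized, Non-blinded, Surgical outcomes, Pilot study assessing clinical outcomes following fat grafting for pain at amputation sites". No other section describes masking of the patient or gives a reason for its absence.

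Section 2.17 lists the primary outcomes as "Improvement of pain at the amputation site, improved ability to tolerate a prosthesis, and generation of a stable volume of adipose tissue", to be compared between two groups of 15. Section 1.1 hypothesises better graft retention and a better result with enrichment. Section 1.3 says the study will examine whether "fat grafting with cell enrichment will demonstrate increased fat retention and decreased pain compared to standard fat grafting alone".

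Pain is recorded by the patient on a form. Under Section 2.6, pre-graft visit, item 6, "The subject will be instructed to document the discomfort to include frequency, location, intensity" on a 1 to 10 scale. Section 2.7, item 11, repeats the limb pain assessment at each post-operative visit.

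The operative visit in Section 2.6 gives one description of anesthesia for everyone ("Subjects will receive general anesthesia or a block with sedation") and one of the harvest, up to 1500 cc of lipoaspirate. Enrichment takes place in a separate laboratory, and its preparation "will add no more than 30 minutes to the overall operating time compared to Autologous Standard fat graft processing".

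**The concern.** The patient is the rater for pain and for most of the function measures. Masking those who read scans or run walking tests would not protect these outcomes. If patients know they received the enriched graft and have been told the trial hopes it works better, they may rate their pain lower for that reason alone. The bias would run in the direction of the hypothesis, on a primary outcome.

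Both arms receive a real graft by the same route, so withholding the arm needs no sham and no added procedure. The plan gives up this protection without saying why.

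**Working it through.** **1. Which outcomes depend on the patient's report (Sections 2.5.1 and 2.7, item 5)**

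- Patient report: PEQ, LEFS, DASH, FMA and prosthetic device use history. That is 5 of the 8 assessments listed a to h.
- Not self-report: 6MWT, AMP and physical examination, 3 of 8.
- Also patient report: the pain form and the SF-36.
- Not open to patient expectation: graft volume on CT or MRI, which is also a primary outcome.

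**2. What differs between arms from the patient's side (Section 2.6)**

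| Feature | Standard | Enriched |
|---|---|---|
| Anesthesia, harvest sites, incisions | as described once for all | same |
| Harvest ceiling | 1500 cc | 1500 cc |
| Sent for cell processing | none | 60-150 cc |
| Research sample | up to 80 cc | up to 80 cc |
| Added operating time | none | at most 30 minutes |
| Stagger | none | 10-14 days between the first six subjects |
| Injection, visits, scans, biopsy time points | common | common |

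The hospital may be a further cue. Three hospitals are named for surgery, while the cell laboratory is described as across the street from the operating room and joined to it by a bridge. The text does not say which of the three fit that description. Each of these differences might hint at the arm, but none requires the patient to be told.

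**3. The plan's own figure (Section 2.18)**

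The plan states a detectable effect of about 0.9 with 30 patients and alpha 0.05. I read its beta of 0.8 as 80% power. For two groups of 15, the detectable d = (z for alpha + z for power) × sqrt(2/15), where sqrt(2/15) = 0.365.

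- One-sided: (1.645 + 0.842) × 0.365 = 0.91, which reproduces the figure.
- Two-sided: (1.960 + 0.842) × 0.365 = 1.02, which does not.

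That statement is about soft-tissue volume. The plan has no power figure for pain, and the present point does not rest on it.

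**4. Illustration of the bias**

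From the documents: 15 per arm and alpha 0.05. Assumed: a two-sided two-sample t-test on pain change, no true difference, SD of change 2 to 2.5 points, and an expectation difference b of 0.5 or 1 point.

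The noncentrality is b / (SD × sqrt(2/15)), with 28 degrees of freedom and critical value 2.048.

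| b | SD | b/SD | Noncentrality | Chance of a significant result |
|---|---|---|---|---|
| 0 | any | 0 | 0 | 5.0% |
| 0.5 | 2.5 | 0.20 | 0.55 | 8.3% |
| 0.5 | 2 | 0.25 | 0.68 | 10.1% |
| 1 | 2.5 | 0.40 | 1.10 | 18.5% |
| 1 | 2 | 0.50 | 1.37 | 26.2% |

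Counting only results that favour enrichment, the chance goes from 2.5% with no bias to 7.6% at 0.2 SD, 18.4% at 0.4 SD and 26.2% at 0.5 SD. Under the one-sided 0.05 test that reproduces the plan's figure, it goes from 5% to 13.3%, 28.2% and 37.9% at the same bias sizes.

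**The case against.** **This is a pilot that declares its non-blinding openly, and its only power statement concerns imaging volume.** Both statements are true. Pain is still a primary outcome to be compared between randomized arms in Section 2.17, and a sound volume result does not correct a biased pain result.

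**A reader might infer that the protocol has patients told their arm.** The text does not say this. Disclosure is inferred from the design label and the lack of any masking step. The consent pages and study schema are not in the copy reviewed.

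**A reader might infer that a pain difference could never be separated from expectation.** That goes too far. Pain can be read beside graft volume, 6MWT, AMP and the examination findings. Section 2.6, item 7, also plans questionnaires on pre-surgical expectations, which might serve as a covariate. This helps only in part, because no instrument is named for it and an expectation measured before surgery does not capture the effect of learning the arm later.

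**A reader might infer that the arms already form a ready-made single blind.** The stagger, added time, laboratory aliquot, possible hospital cue and lighter sedation under a block make that too strong. Masking would be imperfect.

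**Both arms expect benefit, so the differential effect may be small.** This stands as a limit on size. It is why the illustration stops at 0.5 SD.

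**Blinding was already raised.** Section CS1.1.1 records a past board concern about investigators who assess outcomes. That is a different rater from the patient.

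**Conclusion.** The point holds as a design weakness that should be corrected. It is confined to patient-reported outcomes: pain, the reported part of prosthesis tolerance, and the questionnaires. Imaging volume is outside it.

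The direction of the risk follows from the stated hypothesis and needs no assumed SD. The size cannot be known from the documents, which give no SD for pain and no estimate of an expectation effect. Under the stated assumptions, the false-positive rate on pain rises from 5% to about 8-10% for a 0.5-point expectation difference and to about 19-26% for 1 point. The two-sided two-sample test is itself an assumption, since Section 2.18 names paired t-tests and repeated-measures analysis of variance and states no sidedness. The paired before-and-after tests would not remove the bias from the comparison between arms.

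**What to change.** - **Section 2.3:** change the design to participant-masked for every subject not yet told the arm.
- **Sections 2.6, 2.7 and the consent form:** state that the arm is not told to the patient, is not discussed in the operating room under block with sedation, and is not revealed at visits by the PI, co-investigators, coordinator or therapists. Keep it out of discharge papers and, as far as possible, out of record entries the patient can see. Section 2.14 places procedure information in the UPMC record.
- **Cues:** use the same scheduling and hospital rules in both arms as far as possible, leaving the FDA-advised stagger as it is.
- **Disclosure:** tell the patient the arm after POV6, or earlier for a safety need, by a defined route.
- **Check:** ask each patient to guess the arm at POV4 and POV6, and report the guesses with the pain result.
- **Analysis:** report patients already treated open-label separately, in a sensitivity analysis. They cannot be masked afterwards.

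The cost is a protocol and consent amendment that needs IRB approval in a trial run under an IDE. Section 5.13 requires HRPO approval before a significant design change is put into effect. The file is also at a late stage: Section 4.9 shows a consent form from November 2018, and the attachments list an enrollment-hold communication from March 2018. The gain therefore depends on how many patients are still to be treated or told their arm. No sham, extra procedure, extra staff or change in sample size is needed.
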